4. SELECTION OF STUDY POPULATION

4.1 Inclusion Criteria

In order to participate in this study, all subjects must meet ALL of the inclusion criteria described.

1. Individuals of 18 through 55 years of age on the day of informed consent or assent.
2. Individuals who received Menveo 4 to 6 years prior to enrolment at an age of 11 years or older (Menveo-Menveo group)

OR

Individuals who received Menactra 4 to 6 years prior to enrolment at an age of 11 years or older (Menactra-Menveo group)

OR

Individuals who have not received any previous meningococcal vaccine (Naive group).

3. Individuals who have voluntarily given written informed consent (and/or assent, if applicable) after the nature of the study has been explained according to local regulatory requirements, prior to study entry. If the subject is under age 18 at the time of enrolment, the parent(s)/legal guardian(s) of the subject should have voluntarily given written informed consent.
4. Individuals who can comply with study procedures including follow-up¹.

S. Males

Or

Females of non-childbearing potential²

Or

¹ A subject and/or parent(s)/legal guardian(s) is/are considered to be compliant if the Investigator judges that the subject will complete the Subject Diary and return for all the follow-up visits scheduled in the study.

² A female is considered to be of non-childbearing potential prior to menarche and after natural or induced menopause. Natural menopause is recognized to have occurred after 12 consecutive months of amenorrhea for which there is no other obvious pathological or physiological cause. Induced menopause is recognized to have occurred after hysterectomy, after bilateral oophorectomy, or iatrogenic ablation of ovarian function.

Females of childbearing potential who are using an effective birth control method¹ which they intend to use for at least 30 days after the study vaccination

4.2 Exclusion Criteria

Each subject must not have:

1. History of any meningococcal vaccine administration other than the single vaccination given 4 to 6 years before (Menveo-Menveo and Menactra-Menveo groups)

OR

History of any meningococcal vaccine administration (Naive group).

2. Current or previous, confirmed or suspected disease caused by *N. meningitidis*.
3. Household contact with and/or intimate exposure to an individual with any laboratory confirmed *N. meningitidis* infection within 60 days prior to study vaccination
4. Progressive, unstable or uncontrolled clinical conditions.
5. Hypersensitivity, including allergy, to any component of vaccines, medicinal products or medical equipment whose use is foreseen in this study.
6. Clinical conditions representing a contraindication to intramuscular vaccination (IM) and blood draws.
7. Abnormal function of the immune system resulting from:
 - a. Clinical conditions.
 - b. Systemic administration of corticosteroids (PO/IV/IM) for more than 14 consecutive days within 90 days prior to study vaccination
 - c. Administration of antineoplastic and immunomodulating agents or radiotherapy within 90 days prior to study vaccination

¹ The following birth control methods are considered effective:

Abstinence

Hormonal contraceptive (such as oral, injection, transdermal patch, implant) if used for at least 30 days prior to informed consent

Diaphragm preferably with spermicide, tubal occlusion device

Intrauterine device (IUD)

Tubal ligation

Male partner using condom preferably with spermicide

Male partner having been vasectomized at least six months prior to informed consent

8. Received immunoglobulins or any blood products within 180 days prior to informed consent.
9. Received systemic antibiotic treatment (PO/IV/IM) within 3 days prior to study vaccination or blood draw.
10. Received an investigational or non-registered medicinal product within 30 days prior to study vaccination.
11. Study personnel as an immediate family or household member.
12. Individuals who have received any other vaccines within 7 days (for inactivated vaccines) or 14 days (for live vaccines) prior to vaccination in this study or who are planning to receive any vaccine within 28 days from the study vaccination.
13. Individuals who have experienced a moderate or severe acute infection and/or fever defined as a temperature 38°C (100.4°F) within 3 days prior to study vaccination.
14. Any other clinical condition that, in the opinion of the investigator, might pose additional risk to the subject due to participation in the study.

4.3 Criteria for Delay of Vaccination and/or Blood Sampling

There may be instances when individuals meet **all** eligibility criteria for vaccination yet have a transient clinical circumstance which may warrant delay of vaccination: body temperature elevation [38.0° C (100.4° F) within 3 days prior to intended study vaccination], systemic antibiotic treatment within 3 days prior to study vaccination or blood draw. Under such circumstances a subject may be considered eligible for study enrolment after the appropriate window for delay has passed and inclusion/exclusion criteria have been rechecked, and if the subject is confirmed to be eligible.

There is a clinical circumstance that warrants delay of blood collection for immunogenicity assessments in this study subject has received a dose of systemic antibiotics less than 3 days before the intended blood collection. In the event that a subject meets this criterion for delay of blood collection, blood collection may proceed once the window for delay has passed.

5. STUDY PROCEDURES

The sections that follow provide an overview of the procedures that are to be followed in enrolling, evaluating, and following subjects who participate in this clinical study. Visits can be either clinic visits or safety follow-up telephone calls, as specified in the Table below and in the [Time and Events Table 4](#).

Table 5-1 Study Procedures

Visit Category	Procedures
Pre-vaccination Clinic Visit(s)	Section 5.1 describes procedures to be followed prior to study vaccination: informed consent/assent, screening, enrolment, and randomization
Vaccination Clinic Visit(s)	Section 5.2 describes procedures to be followed during each clinic visit involving vaccination: vaccination, post-vaccination procedures, and post-vaccination reminders
Post-vaccination Visit(s)	Section 5.3 describes follow-up clinic visits and safety follow-up calls
Unscheduled Visit(s)	Section 5.4 Unscheduled visits are not expected within this protocol.
Study Termination Visit	Section 5.5 describes procedures to be followed at the last study visit for a subject (may include early termination visit)

5.1 Pre-vaccination Clinic Visit(s)

This section describes the procedures that must be performed for each potential subject prior to vaccination, including obtaining informed consent/assent, screening, enrolment and randomization.

5.1.1 Informed Consent/Assent

"Informed consent" is the voluntary agreement of an individual or his/her legal guardian(s) to participate in research. Consent must be given with free will of choice, and without undue inducement. The individual must have sufficient knowledge and understanding of the nature of the proposed research, the anticipated risks and potential benefits, and the requirements of the research to be able to make an informed decision.

"Assent" is a term used to express willingness to participate in research by persons who are by definition too young to give informed consent but who are old enough to

understand the proposed research in general, its expected risks and possible benefits, and the activities expected of them as subjects. Assent by itself is not sufficient, however. If assent is given, informed consent must still be obtained from the subject's parent(s) or legal guardian(s). Local laws define who constitutes a "child," and such definitions dictate whether or not a person can legally consent to participate in a protocol (Levine 1988).

Info111led consent of the parent(s)/legal guardian(s) and assent of subject following local IRB/EC guidance **must** be obtained before conducting any study-specific procedures (i.e., all of the procedures described in the protocol). The process of obtaining informed consent and assent should be documented in the subject source document in addition to maintaining a copy of the signed and dated informed consent. Additional specifics regarding the informed consent and assent processes are located in [section 13.2, Info111led Consent Procedures](#).

If a subject and/or parent(s)/legal guardian(s) is unable to read, an impartial witness should be present during the entire informed consent and assent discussion. An impartial witness is defined as a person who is independent from study conduct, who cannot be unfairly influenced by those involved with the study, who attends the informed consent process if the subject or the subject's legally acceptable representative cannot read, and who reads the informed consent form and any other written information supplied to the subject. After the written informed consent form and any other written information to be provided to subjects, is read and explained to the subject and/or parent(s)/legal guardian(s) and after the subject and/or parent(s)/legal guardian(s) has verbally consented to the subject's participation in the study and, if capable of doing so, has signed and personally dated the informed consent fo111, the witness should sign and personally date the consent form. By signing the consent fo111, the witness attests that the information in the consent form and any other written information was accurately explained to, and apparently understood by, the subject and/or parent(s)/legal guardian(s) and that informed consent was freely given by the subject and/or parent(s)/legal guardian(s).

5.1.2 Screening

Subject identification numbers will be assigned sequentially to the subjects who have consented to participate in the study, according to the range of subject identification numbers allocated to each study center. The eligibility of the subject will be determined based on the inclusion and exclusion criteria listed in [section 4, Selection of Study Population](#) and evaluated during this screening procedure.

Prior to study enrolment, demographic data will be collected from the subject, including: date of birth, gender, race, ethnicity, prior vaccination against meningitis. Note: Appropriate written documentation of the brand of primary vaccination (Menveo or Menactra) and vaccination date must be provided prior to enrollment.

Medical history will also be collected, including but not limited to any medical history that may be relevant to subject eligibility for study participation such as prior vaccinations, concomitant medications, and previous and ongoing illnesses or injuries. Relevant medical history can also include any medical history that contributes to the understanding of an adverse event that occurs during study participation, if it represents an exacerbation of an underlying disease/pre-existing problem.

Review of systems is a structured interview that queries the subject and/or parent(s)/legal guardian(s) as to any complaints the subject has experienced across each organ system. This will be performed before enrolment and used to guide physical examination.

If applicable, prior and concomitant medications or vaccinations taken prior to start of study should be collected (refer to [section 6.5, Prior and Concomitant Medications and Vaccines](#) for further details).

Collect vital signs (heartrate, blood pressure, and temperature (preferably taken orally). Measure height and weight.

Perform pregnancy testing in women of childbearing potential (refer to [section 3.5, Collection of Clinical Specimens](#) for additional information)

A general physical examination is to be performed by a qualified health care practitioner. "Qualified health care practitioner" refers to any licensed health care professional who is permitted by institutional policy to perform physical examinations and who is identified within the Study Staff Signature Log.

The data collected through study assessments listed above will be written in the source document (see [section 9.1, Source Documentation](#)). Should the physical assessment reveal any abnormal values or events, these must be documented in the CRF Adverse Events Form

Prior to vaccination, approximately 10 mL of blood will be drawn from all subjects for the immunological testing see [section 3.5, Collection of Clinical Specimens](#).

In the event that the individual is determined ineligible for study participation he/she is considered a screen failure. The reason for screen failure must be documented in the Screening and Enrolment log. If the individual is determined to be eligible for the study, he/she will be enrolled into the study.

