7. ASSESSMENTS

7.1 Safety Assessment

The measures of safety used in this study are routine clinical procedures. They include a close vigilance for, and stringent reporting of, selected local and systemic adverse events routinely monitored in vaccine clinical studies as indicators of reactogenicity.

An adverse event (AE) is defined as any untoward medical occurrence in a subject or clinical investigation subject administered a pharmaceutical product at any dose that does not necessarily have to have a causal relationship with this treatment. Therefore, an AE can be any unfavorable and unintended sign (including an abnormal laboratory finding, for example), symptom, or disease temporally associated with the use of an investigational product, whether or not considered related to the investigational product. This definition includes intercurrent illnesses or injuries and exacerbation of pre-existing conditions.

The period of observation for AEs extends from the time the subject signs informed consent until he or she completes the specified safety follow-up period of 180 days or terminates the study early (whichever comes first). AEs occurring after the informed consent form is signed but prior to receiving study vaccine/product will be documented as an adverse event and recorded within source document. However, any AEs occurring prior to receipt of any study vaccine will be analyzed separately from "treatment emergent" AEs (AEs occurring after administration of the first study vaccine).

Adverse events are collected as either solicited or unsolicited adverse events. Solicited events are derived from organized data collection systems, such as Subject Diaries.

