8.4.3.1.3 Analysis of Unspecified Adverse Events

This analysis applies to all adverse events occurring during the study, judged either as probably related, possibly related, or not related to vaccination by the investigator, recorded in AE CRF, with a start date on or after the date of first vaccination. AE starting prior to the first vaccination will only be listed. The original verbatim terms used by investigators to identify adverse events in the CRFs will be mapped to preferred terms using the MedDRA dictionary. The adverse events will then be grouped by MedDRA preferred terms into frequency tables according to system/organ class (SOC).

All reported adverse events, as well as adverse events judged by the investigator as at least possibly related to study vaccine, will be summarized according to SOC and preferred term within SOC. These summaries will be presented by study group and by interval of study observation. When an adverse event occurs more than once for a subject, the maximal severity and strongest relationship to the vaccine will be counted.

Separate summaries will be produced for the following categories:

- Adverse events that are possibly or probably related to vaccine
- Unsolicited AEs reported within 30 minutes after vaccination
- Unsolicited AEs reported within 29 days after vaccination
- Adverse events leading to withdrawal
- Adverse events leading to a medically attended visit
- Serious adverse events
-

Data listings of all adverse events will be provided by subject. In addition, adverse events in the categories above will be provided as listed data.

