6.4.2.3. Unsolicited Adverse Events

All AEs occurring during the first 28 days after vaccination, including the day of vaccination, and all medically attended unsolicited adverse events, adverse events leading to study withdrawal and serious adverse events occurring at any time during the study will be recorded according to the protocol-specified reporting rules.

Only vaccine-emergent adverse events (see [section 11.2](#) for definition) will be analyzed, i.e., excluding those after a subject has given informed consent but before vaccination. The selection of unsolicited adverse events and the assignment to time intervals will be done by day of onset and not by days ongoing/persisting.

The analysis of unsolicited adverse events comprises the following categories:

- Any unsolicited adverse event.
- Possibly or probably related unsolicited adverse events.
- Unsolicited adverse events leading to death.
- Serious adverse events.
- Possibly or probably related serious adverse event.
- Unsolicited adverse events leading to premature withdrawal from study.
- Unsolicited adverse events leading to hospitalization.
- Medically attended adverse events.

Solicited adverse events continuing beyond day 7 will be coded by MedDRA and combined with the respective unsolicited adverse events.

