11.2. Standard data derivation

Immunogenicity

Values below the limit of quantification (recorded as “< LQ”) will be set to half that limit.

Statistical Analysis Plan

| | | |
|--|------------|------------------|
| Study alias & e-track number(s): V59 77 (205352) | Version: 1 | Date: 19-09-2016 |
|--|------------|------------------|

 GSK GlaxoSmithKline

Seroresponse is defined for this booster study as follows:

- for subjects with pre-vaccination titers <4, post-vaccination titers \geq 16;
- for subjects with pre-vaccination titers \geq 4, post vaccination titers at least 4 times the pre-vaccination titers.

Duration in the Study

Duration in the study is defined in days as:

Last visit date (visit x)^a – Enrollment date (visit 1) + 1

^aor premature discontinuation date (in case of withdrawal from the study)

The duration is missing if one of the dates is missing or incomplete.

Unsolicited Adverse Events

All adverse events will be characterized according to the date of occurrence related to the vaccination phase as follows:

- **Emergence before vaccination phase:** start date before the first date of injection of study vaccine.
- **Emergence during vaccination phase:** start date on or after the first date of injection of study vaccine or, adverse event increase in severity including to “serious” adverse event.

If start date is equal to the first date of injection then “timing” variable (“On injection day, before injection”/“On injection day, after injection”) will be used to define whether the adverse event occur before or after the injection.

If an adverse event start date is missing or unknown, the adverse event will be considered as emergent.

When start and/or end dates of an adverse event are only partially known, adverse events will be categorized as emergent before, during, or after vaccination phase using the following rules:

Statistical Analysis Plan

| | | |
|--|------------|------------------|
| Study alias & e-track number(s): V59 77 (205352) | Version: 1 | Date: 19-09-2016 |
|--|------------|------------------|

 GSK GlaxoSmithKline

- If the partial end date is before ($<$) the first study vaccination (i.e., year or year & month is/are before the first study vaccination year or year & month) then the adverse event is emergent before vaccination phase.

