- If the partial start date is equal or after (\geq) the first study vaccination (i.e., year or year & month is/are after or the same as the first study injection year or year & month) then the adverse event is emergent during vaccination phase.

The **maximum event severity** is the greatest severity associated with a preferred term for a reported adverse event according to the following order: Mild < Moderate < Severe. Unknown/ Missing severity is considered as severe (except for the definition of emergence).

Multiple AEs with the same PT for the same subject are counted only once.

Vaccination-related Adverse Events are those for which the cause has been evaluated by the investigator, and recorded either as possibly related, probably related or unknown/missing.

Prestudy, Concomitant and Post-Vaccination Medications

A previous medication is a medication used only before the first study vaccination (i.e. medication end date < first study vaccination date).

A post-vaccination medication is a medication used only after study vaccination + 28 days (i.e. medication start date $>$ last study vaccination date + 28 days).

All other medications are concomitant

When start and/or end dates of a medication intake are missing, the medication is considered as concomitant with the study vaccination schedule.

If the first study vaccination date is missing then the medication is considered as concomitant with the study vaccination schedule, provided that the study vaccine was administered to the subject.

The business rule can be consulting by clicking on the following icon:

| | | | |
|--|------------------|---|--|
| Statistical Analysis Plan | |  GlaxoSmithKline | |
| Study alias & e-track number(s): V59 77 (205352) | | | |
| Version: 1 | Date: 19-09-2016 | | |

 NV business
 rule.docx

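### Ongoing findings from the pre-vaccination exam can be counted as vaccine-emergent AEs when their onset is unknown or only partly dated in the vaccination year or month

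*Protocol*

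**What the plan says.** **Recording.** Protocol 5.1.2 covers procedures before vaccination. After vital signs and a general physical examination it instructs: "Should the physical assessment reveal any abnormal values or events, these must be documented in the CRF Adverse Events Form". The same section collects medical history, including "previous and ongoing illnesses or injuries".

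**Intent for pre-vaccination events.** Protocol 7.1 starts AE observation early: "The period of observation for AEs extends from the time the subject signs informed consent". It adds that "any AEs occurring prior to receipt of any study vaccine will be analyzed separately from" treatment-emergent AEs. Protocol 8.4.3.1.3 and SAP 6.4.1 share a tabulation rule: "AE starting prior to the first vaccination will only be listed". SAP 6.4.2.3 restricts the analysis to vaccine-emergent AEs, "i.e., excluding those after a subject has given informed consent but before vaccination", and refers to SAP 11.2 for the definition.

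**Classification.** SAP 11.2 sorts AEs by start date relative to injection. When the two dates coincide, a timing variable separates before from after. Two further rules handle poor dates. The first is "If an adverse event start date is missing or unknown, the adverse event will be considered as emergent". The second begins "If the partial start date is equal or after" and makes an AE emergent when its year, or year and month, is the same as or later than that of vaccination. A partial end date before vaccination makes the AE emergent before vaccination.

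**The concern.** A finding written down at an exam held before injection was present before injection, whatever is known about when it began. SAP 11.2 never uses that fact. It looks only at dates, and a finding noticed for the first time at an exam is one whose onset date may well be unknown.

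The partial-date route is also realistic. The Time and Events Table allows screening from Day -5 to Day 1, so a finding dated by the month in which it was noticed will usually carry the vaccination month. A year-only date in the vaccination year has the same effect.

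The frequency of unsolicited AEs is a secondary safety endpoint. It is reported as percentages within groups, with no between-group tests, so the absolute percentages are the result. Two other SAP 11.2 defaults could add to the error if those fields are also blank: missing severity counts as severe, and missing causality counts as vaccination-related.

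**Working it through.** The plan states no figure to reproduce, so the check passes an exam finding entered on the AE form through the SAP 11.2 rules, once for each state its dates can take.

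1. Full start date before injection: emergent before vaccination, listed only. Correct.
2. Start date on injection day, timing flagged as before injection: emergent before vaccination, listed only. Correct.
3. Partial start date in an earlier year or month: not caught by the partial-start rule and before vaccination under the general definition, so listed only. Correct.
4. Partial start date in the same year, or the same year and month, as injection: emergent. Wrong for a finding seen before injection.
5. Start date missing or unknown, finding ongoing: emergent. Wrong. The partial end-date rule cannot help because there is no end date.
6. Start date unknown, partial end date before the vaccination year or month: the missing-start rule says emergent and the end-date rule says before vaccination. The SAP gives no order of precedence, so the result is undetermined.

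Misclassification occurs in states 4 and 5, possibly in 6, and not in 1 to 3.

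The safeguards elsewhere do not catch states 4 and 5. The list-only rule in Protocol 8.4.3.1.3 and SAP 6.4.1 depends on the AE starting before vaccination. SAP 6.4.2.3 takes its definition of emergent from 11.2. The timing variable applies only when the start date equals the injection date.

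**Size.** The inputs are the planned group sizes in Protocol 3.1: 300, 300 and 100. If k subjects in a group of n are misclassified and have no other AE, the any-unsolicited-AE percentage rises by 100 × k / n points.

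- k = 1, n = 300: 100 × 1 / 300 = 0.33 points.
- k = 1, n = 100 (Naive): 100 × 1 / 100 = 1 point.
- k = 5, purely as an illustration: 100 × 5 / 300 = 1.67 points, and 100 × 5 / 100 = 5 points.

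The documents give no rate of abnormal screening exams and no rate of unknown or partial onset dates, so k cannot be derived. These increments are upper bounds: a misclassified subject who also has a genuine emergent AE adds nothing to the any-AE row, although the affected preferred term still gains a count.

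**The case against.** The plan says repeatedly that pre-vaccination events stay out of the tables, and SAP 11.2 achieves this for three of the six date states. A long-standing condition would naturally be entered with an earlier year, which is handled correctly. Treating an unknown onset as emergent is a recognised conservative default, because it over-counts rather than hides events. Missing dates can be queried, all AEs are listed by subject, and SAP 11.2 points to an attached business-rule file that cannot be read here and may say more. All of this narrows the point. It does not remove states 4 and 5, where the default is applied to a finding whose presence before injection is documented.

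A further objection stands in part. SAP 6.4.2.3 assigns AEs to intervals by day of onset, and an event without an onset day has none to assign. It is therefore not shown that every such event reaches the Day 1 to Day 29 count. What is shown is that it is classed as emergent and so is eligible for tabulation.

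A reader might infer four stronger things that the documents do not support:

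- That pre-existing conditions in general are tabulated as emergent. States 1 to 3 show otherwise.
- That Protocol 7.1 admits only exacerbations of pre-existing conditions as AEs. It says the definition includes them, and it requires events between consent and vaccination to be documented as AEs.
- That these findings drop out of the medical-history table. Nothing says an AE entry replaces a medical-history entry.
- That group comparisons are biased. The rule is the same in every group, the synopsis asks for Naive subjects of similar age, and no statistical comparison of safety is planned.

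**Conclusion.** The point holds in a limited form. Ongoing findings documented before injection can be classed as vaccine-emergent unsolicited AEs when the start date is missing or unknown, or partial and in the vaccination year or month. That contradicts the stated intent of Protocol 7.1 and SAP 6.4.2.3. Findings with any earlier date, or flagged as before injection on the day, are unaffected.

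The effect is on absolute unsolicited AE percentages, at the per-subject sizes shown above, and the total cannot be computed from the documents. The conclusion assumes that sites follow Protocol 5.1.2 as written and that no rule in the unseen business-rule file or the CRF completion instructions overrides SAP 11.2. The primary objective is unaffected. The change is worth making because a stated rule gives a wrong classification in a secondary safety endpoint and the correction costs almost nothing.

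**What to change.** **SAP 11.2.** Add that an AE first documented at a pre-vaccination assessment is classed as emergent before vaccination, whatever the completeness of its start date, unless it worsens after injection. State that this rule takes precedence over the missing and partial start-date rules. That also settles state 6 for these findings.

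**Protocol 5.1.2.** Replace the instruction so that pre-existing findings at the pre-vaccination exam are recorded as medical history, and the AE form is used only for findings that began or worsened after consent. This matches Protocol 7.1.4, which already sends a pre-existing condition that results in hospitalisation to the Medical History CRF.

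The cost is an addition to the SAP, one protocol sentence and a matching CRF completion instruction. No new data, visits or analyses are needed. If a protocol amendment is not practical, the SAP rule alone removes the misclassification, provided the data show that an AE was first recorded at a pre-vaccination assessment.
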